7.5.1. Prohibited Medications and Restricted Concomitant Medications

Prohibited medications and restrictions are detailed in Table 5. Refer to the prescribing information for the study drug ([Abilify USPI](#) ; [Aristada USPI](#) ; [Initio USPI](#)) and each concomitant medication for interactions and dose restrictions.

Concomitant use of potent oral CYP3A4 inhibitors **and** CYP2D6 inhibitors is to be avoided. In addition, patients with known CYP2D6 poor metabolism should not receive strong oral CYP3A4 inhibitors during the study. During the study, dose adjustment may be necessary in the event of use of potent oral CYP2D6 inhibitor, or a CYP3A4 inhibitor or inducer. For example, the use of CYP3A4 inducers may require dose escalation. Investigators should consult the prescribing information for questions regarding any such dose adjustments.

Table 5: Prohibited Medications: Pre- and Post-randomization

Class (medication)	Prescribed before randomization	Started Post-randomization
Antipsychotics		
Other first-line oral antipsychotic	all prior (non-aripiprazole) antipsychotics must be discontinued within 2 weeks prior to the Randomization visit	Not allowed ¹²³
Clozapine	Not allowed	Not allowed
Other long-acting injectables	Not allowed	Not allowed
Antidepressants		

Class (medication)	Prescribed before randomization	Started Post-randomization
	Generally allowed but sertraline (Zoloft®), citalopram (Celexa®) or escitalopram (Lexapro®) preferred	Sertraline (Zoloft®), citalopram (Celexa®) or escitalopram (Lexapro®) preferred
Mood Stabilizers (Starting mood stabilizer not encouraged)		
Lithium carbonate	Allowed	Allowed
Lamotrigine	Allowed	Allowed
Valproate	Allowed for men Not allowed for women	Allowed for men Not allowed for women
Carbamazepine/oxcarbazepine	Not allowed	Not allowed
Anti-anxiety medications		
Lorazepam PRN anxiety/insomnia	Allowed	Allowed ⁴
Lorazepam standing	Allowed	Allowed
Clonazepam PRN	Not allowed	Not allowed
Clonazepam standing	Allowed ⁵	Allowed
Alprazolam	Not allowed	Not allowed
Diphenhydramine (for insomnia)	Allowed ⁶	Allowed
Anti-EPS and anti-akathisia		
Propranolol (akathisia only)	Allowed	Allowed/preferred
Lorazepam (akathisia or acute dystonia only)	Allowed	Allowed
Benztropine (antipsychotic-induced parkinsonism)	Allowed	Allowed
Diphenhydramine (akathisia and acute dystonia only)	Allowed	Allowed
ADHD therapies		
Methylphenidate-based ADHD treatments	Allowed with review	Not allowed
Amphetamine-based ADHD treatments	Not allowed	Not allowed

Abbreviations: PRN= as needed; ADHD= Attention-deficit/hyperactivity disorder; EPS= Extrapyramidal symptoms

¹ For patients in the ARI-ORAL arm, dose increases for persistent symptoms and/or symptom exacerbations is permitted. However, prescribing another non-ariPIPRAZOLE oral antipsychotic for “rescue” medication will be criteria for stopping the treatment assignment.

² For patients in the AL-LAI arm, ARI-ORAL for \leq 2 weeks will be allowed for transient exacerbations that are deemed to be caused by external stressors. ARI-ORAL prescribed for $>$ 2 weeks will be criteria for AL-LAI failure

³ Patients receiving up to 2 days of oral or short acting antipsychotic IM medication because they presented to an ER or crisis facility outside of the UCLA program will not be criteria for discontinuation of treatment assignment

⁴ Maximum 4mg day Total Daily Dose (TDD)

⁵ Maximum is 3mg/day Total Daily Dose (TDD)

⁶ Max 100mg

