Criteria for Efficacy Evaluation: Primary Endpoint The primary endpoint will be time to first positive symptom exacerbation and/or relapse following a period of absence or relatively low levels of psychotic symptoms based on the expanded 24-item version Brief Psychiatric Rating Scale. Secondary Endpoints Functional assessment: The Role ratings on the Global Functioning Scale (GFS: Role) will serve as the measure of functional outcome. The GFS: ROLE will be administered every three months throughout the 12-month Treatment period. Cognitive assessment: The Overall Composite T-score from the MATRICS Consensus Cognitive Battery (MCCB) will be the overall index of cognitive performance. The MCCB will be administered every six months throughout the 12-month Treatment period. Exploratory Endpoints Endpoints include Quality of Life, negative symptoms, self-reported awareness of having a mental disorder, service engagement, prolactin-related side effects, treatment satisfaction, and family/caregiver medication administration burden. Safety Assessments Extrapyramidal symptoms will be assessed on three scales (Abnormal Involuntary Movement Scale, Barnes Akathisia Rating Scale, and the Extrapyramidal Symptom Rating Scale). Adverse events (including serious and AEs of special interest), and suicidality will be monitored.
Statistical methods: Sample Size Considerations: Ninety first-episode patients will be randomized (1:1) fashion to either AL-LAI or ARI-ORAL, and based on our previous RCT, assume a 20% attrition rate over 12 months. 45 randomized patients (36 completers) in each group provides at least 80% power. Statistical power considerations are based on the effect sizes observed when comparing long-acting injectable risperidone vs oral risperidone (survival analysis for psychotic relapse: 5% relapse in the risperidone long-acting injectable group and 33% relapse in the oral risperidone group). On the basis of hazard function rates of 5.0% (AL-LAI)

and 33% (ARI-ORAL), the study has 87% power ($\alpha=0.05$). On a more conservative basis of hazard function rates of 7.5% (AL-LAI) and 33% (ARI-ORAL), the study has 78% power ($\alpha=0.05$).

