7.4.5. Prior and Concomitant Medication Review

At Screening, all medications (prescription and nonprescription, including vitamins and herbal supplements) taken by a given patient within 30 days prior to screening through follow-up will be recorded. At all other time point(s) specified in [Table 2](#), prospective patients will be asked about the medications they have taken since the last visit and are currently taking (including prescription and nonprescription medications, vitamins, and supplements).

The Investigator will record the following data on all medications used by the patient: name, dose, regimen, route of administration, start and stop dates, and the indication for use.

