12.3. Demographics and Baseline Data

Demographics and baseline characteristics such as gender, age, race, weight, height, and body-mass index will be summarized using descriptive statistics. Medical history will be summarized using the number of observations and percentage of patients reporting each category. Concomitant medications as well as any protocol deviations will be recorded.

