12.5. Safety and Tolerability Analyses

The following safety and tolerability measures monitored throughout the study and summarized:

- AEs
- EPS Scales (AIMS, BARS, and ESRS-A)
- Presence of akathisia
- C-SSRS

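### Section 12.5 summarises EPS scale scores without regard to the anti-EPS and anti-akathisia drugs that Table 5 permits, so scores taken on treatment can blur a tolerability difference between arms

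*Combined protocol and SAP*

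**What the plan says.** **Permitted drugs.** Table 5 has a block for anti-EPS and anti-akathisia treatment. Propranolol, lorazepam, benztropine and diphenhydramine are each permitted before and after randomisation, with the indication written into the row. One row begins "Propranolol (akathisia only" and is marked as preferred after randomisation; another begins "Benztropine (antipsychotic-induced parkinsonism". Section 8.3.2.1 keeps anti-EPS drugs already in use going for at least 30 days before taper is considered.

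**Assessment.** The synopsis states: "Extrapyramidal symptoms will be assessed on three scales". Section 7.4.9.2 uses AIMS mainly for dyskinesia, BARS for akathisia, and ESRS-A for parkinsonism and dystonia. It also calls for an unscheduled rating when a patient complains of EPS between scheduled ones. In Table 2, ESRS and AIMS fall at Screening, Day 1, Months 6 and 12, and the Month 13 follow-up. The Month 12 column also serves as the end-of-treatment rating. BARS is scheduled at those points and also in Months 1-5 and 7-11.

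**Analysis.** Section 12.5 opens with "The following safety and tolerability measures monitored throughout the study and summarized" and lists adverse events, "EPS Scales (AIMS, BARS, and ESRS-A", "Presence of akathisia" and the C-SSRS. Under Section 7.4.5 the investigator records "name, dose, regimen, route of administration, start and stop dates, and the indication for use" for every medication. Section 12.3 is the only statistical section that mentions these data: "Concomitant medications as well as any protocol deviations will be recorded". No section plans a by-arm summary of anti-EPS drug use or says how a scale score obtained on such a drug is to be treated.

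**The concern.** Section 5.3 makes tolerability a comparison between the two arms. A scale score measures the symptoms left after treatment. If a patient's parkinsonism appears and is then controlled with a permitted drug before the next scheduled ESRS-A, the score records little or nothing, and the continuing need for the drug appears in no table.

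Two consequences follow. If treatment is equally effective in both arms, a real difference shrinks. If the share of cases treated differs by arm, the scales can show a difference that does not exist or hide one that does.

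Unequal treatment is possible here, though this is inference. The trial is open-label, and oral doses are adjusted at the psychiatrist's discretion while injections run monthly to every two months. Section 9.2.2 describes voucher cover for side-effect drugs only under the oral arm.

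Day 1 scores may be affected too. Section 7.1 requires at least two weeks on oral aripiprazole before randomisation, which is shorter than the 30 days for which a carried-over anti-EPS drug is kept.

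**Working it through.** The plan gives no EPS rate, threshold or power for tolerability, so there is no figure to reproduce. The check has two parts.

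**1. Which scales are exposed**

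| Scale (main use, Section 7.4.9.2) | Scheduled after Day 1 (Table 2) | Table 5 drugs listed for that use | Exposure |
|---|---|---|---|
| ESRS-A (parkinsonism, dystonia) | Months 6, 12, 13 | benztropine; lorazepam and diphenhydramine for acute dystonia | main |
| BARS (akathisia) | Months 1-5, 6, 7-11, 12, 13 | propranolol, lorazepam, diphenhydramine | weaker for onset |
| AIMS (dyskinesia) | Months 6, 12, 13 | none | little |

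A parkinsonism episode treated in Month 2 can be controlled by the Month 6 rating. An akathisia episode has a scheduled BARS in the months between. For both, continuing drug need goes unreported.

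**2. Illustration of the mechanism (all rates assumed)**

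Visible rate = true rate × (1 − share suppressed at rating visits). Take true EPS rates of 30% and 15%, with the same share suppressed in each arm. As a gauge only, power is for two proportions at 45 per arm (Section 6), two-sided 0.05, normal approximation with pooled variance under the null. Section 12.5 itself plans no test.

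| Share suppressed | Visible rates | Difference | Power |
|---|---|---|---|
| 0% | 30% vs 15% | 15 points | 40% |
| 25% | 22.5% vs 11.25% | 11.25 | 29% |
| 50% | 15% vs 7.5% | 7.5 | 20% |
| 75% | 7.5% vs 3.75% | 3.75 | 12% |

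If only the worse arm is treated, 50% suppression gives 0.30 × 0.5 = 15% against 15%, and the difference disappears.

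Now take equal true rates of 25%, with 40% of cases treated in one arm and 70% in the other:

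- If every treated case scores negative: 0.25 × (1 − 0.40) = 15% and 0.25 × (1 − 0.70) = 7.5%, a false gap of 7.5 points.
- If 70% of treated cases score negative: 0.25 × (1 − 0.40 × 0.70) = 18% and 0.25 × (1 − 0.70 × 0.70) = 12.75%, a false gap of 5.25 points.

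These figures show direction and sensitivity. They describe scale scores alone and leave out adverse event capture. They are not estimates for this trial.

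**The case against.** The strongest reply is that the scales do not stand alone. Adverse events are the first item in Section 12.5 and are collected from consent to the final visit (Section 7.4.12). EPS that leads to a new prescription fits the definition in Section 11.1, so it should be counted whatever a later scale score shows. Presence of akathisia is listed separately. Complaints trigger unscheduled ratings. The patient-completed GASS, the Modified MSQ side-effect item and the recorded reasons for discontinuation add further tolerability evidence.

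Much of this stands. A reader might infer that the plan judges EPS on rating scales alone, or that Table 5 allows these drugs without restriction. Neither is right: Section 12.5 goes beyond the scales, and every anti-EPS row is limited by indication. A reader might also assume that treatment has usually begun before Month 6. The documents give no timing.

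What remains is narrower. Section 12.5 defines no EPS grouping for adverse events and gives no source or definition for presence of akathisia. The GASS is scheduled only at Day 1, Month 6 and Month 12, so it is open to the same masking. An unscheduled rating or an adverse event can mark onset, but neither shows how many patients in each arm needed continuing treatment.

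**Conclusion.** The point holds as a minor gap in the analysis plan, not in data collection. EPS scale summaries that ignore permitted treatment can understate or distort a between-arm difference, chiefly for parkinsonism and dystonia on the ESRS-A and less for akathisia.

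The size in this trial cannot be derived from the documents. It depends on the true EPS rates, the share of cases treated in each arm and how well treatment suppresses the scores, and none of these is given.

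A reader might go further and infer that a less tolerable arm will look equally tolerable. The documents do not support that, because adverse event reporting may reveal the difference. Nor does the point reach the primary endpoint, which is based on BPRS items, or the two secondary endpoints. Only exploratory and safety conclusions on tolerability are affected.

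**What to change.** In Section 12.5, add the following by arm, taken from the Section 7.4.5 concomitant medication record:

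- The number and proportion of patients who start or increase an anti-EPS or anti-akathisia drug after randomisation, using the recorded indication.
- A separate count of patients already on such a drug at Day 1.
- EPS and akathisia adverse events in the same table.
- AIMS, BARS and ESRS-A summaries flagged by whether the patient was on such a drug at the rating.

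Voucher billing should not be the source, because Section 9.2.2 describes it only for the oral arm. Table 5 also permits lorazepam and diphenhydramine for anxiety or insomnia, and an indication-based count will miss any masking from that use. The on-drug flag should therefore cover use of the listed drugs for any indication.

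A composite (scale-positive at a scheduled rating, or treated for that indication) may be added as supportive only. Its scale threshold must be fixed before analysis, since the documents give none. Restricting it to scheduled ratings avoids dependence on complaint-triggered ratings, whose number may differ by arm.

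The cost is a little extra tabulation from data already collected. The limitation is that a treatment start is an open-label prescribing decision, so it should be read beside the scales and adverse events, not in place of them. Permitted drugs, visits and care stay as they are.

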7.5.2. Contraception and Pregnancy

All male and female patients must agree to use an acceptable method of contraception for the duration of the study and 30 days after the final dose of oral study drug, and 90 days following the final dose of long-acting injectable antipsychotic unless they are surgically sterile or postmenopausal (see below). The following are considered acceptable methods of contraception:

1. Double-barrier protection (eg, a condom with spermicide or a diaphragm with spermicide)
2. Intrauterine device
3. Oral contraceptive pills or other hormonal methods (eg, a vaginal ring, contraceptive patch, contraceptive implant); oral contraceptives should have been initiated at least 30 days prior to Screening.

Patients who are abstinent are eligible, provided they agree to use an acceptable contraceptive method should they become sexually active.

Patients who are surgically sterile are exempt from the requirement to use contraception. Women who have undergone a hysterectomy, bilateral tubal ligation, or bilateral salpingo-oophorectomy are considered surgically sterile. Men who have undergone a vasectomy or bilateral orchiectomy are considered surgically sterile. Partner vasectomy is not considered an approved acceptable method of contraception for a female patient.

If a patient becomes pregnant while participating in the study, she will be promptly discontinued from study drug. Pregnancy is not considered an AE, however pregnancy, whether a female study patient or the partner of a male study patient, must be immediately documented on a Pregnancy Form and reported to Alkermes, Inc., within 24 hours of the Investigator becoming aware of the pregnancy as outlined in Section 11.3. Additional follow-up may be required.

The pregnancy will be followed until completion or termination, if feasible. If the outcome of the pregnancy meets the criteria for classification as a SAE it should be reported following the SAE procedure (Section 11.3).

8. TREATMENT OF PATIENTS

Each patient will be provided a prescribing psychiatrist and a case manager/therapist to monitor clinical status and provide treatment. Study visits will occur weekly at Screening and Stabilization period, and then every two weeks throughout the 12-month randomized Treatment period (at each clinical visit and between each clinical visit). The total study duration for each patient will be approximately 70 weeks, including a Screening period (up to four weeks), up to 90-day Stabilization period, and a 12-month randomized Treatment period.

If the patient is not already on ARI-ORAL at Screening, any prestudy oral antipsychotic medication can begin to be tapered off during the Stabilization period, while ARI-ORAL is initiated. During the Stabilization period, all patients will receive flexible dosing of ARI-ORAL. Patients who find ARI-ORAL intolerable during the Stabilization period will not be randomized.

8.1. Study Drug Dose and Administration

During the 12-month Treatment period, patients who tolerate the study medication but find that after adequate duration and dosage, it is inadequately efficacious per clinical judgment, may be switched to another oral antipsychotic at the discretion of the Investigator. Patients who miss scheduled injections or visits are allowed to continue in the same assigned treatment group.

8.1.1. AL-LAI and AL-NCD Administration

Refer to the prescribing information for AL-NCD administration ([Initio USPI](#)). Administer 675mg AL-NCD in either the deltoid or gluteal muscle.

Refer to the prescribing information for AL-LAI administration ([Aristada USPI](#)). In summary, administer AL-LAI either in the deltoid muscle (441 mg dose only) or gluteal muscle (441 mg, 662 mg, 882 mg or 1064 mg) ([Table 6](#)). Clinical staff administering AL-LAI will be licensed to give IM injections in the state of California and will be trained and certified on proper injection technique for AL-LAI and AL-NCD administration.

Table 6: AL-LAI Dosing Frequency and Site of Injection

Dose	Dosing Frequency	Site of Intramuscular Injection
441 mg	Monthly	Deltoid or Gluteal
662 mg	Monthly	Gluteal
882 mg	Monthly or every 6 weeks	Gluteal
1064 mg	Every two months	Gluteal

Refer to the current prescribing information for ARISTADA for the recommended starting dose based on ARI-ORAL total daily dose, handling of missed doses of AL-LAI, early dosing of AL-LAI and dose adjustments for CYP450 considerations for AL-LAI ([Aristada USPI](#)).

Schedule changes, from monthly to every six weeks (or the reverse) will also be allowed after the second injection. Dose changes due to the medical need to initiate concomitant CYP modulators may be performed at any time if the concomitant medication is necessary for more than two weeks.

8.1.2. ARI-ORAL Drug Dose and Administration

Patients in the ARI-ORAL group will receive vouchers that will need to be given to the pharmacy at the time that the study oral antipsychotic medication is first dispensed. When ARI-ORAL is prescribed, the generic formulation will be prescribed, instead of the commercially available Abilify® brand. This voucher will have instructions for the pharmacy to bill Alkermes directly for the medication. Pharmacy billing will also be captured by Alkermes and shared with the study team for use as medication possession data, which will be an additional source of information used to make medication adherence ratings for the ARI-ORAL group patients.

8.2. Measurement of Medication Treatment Adherence

All study drug injections will be directly administered by clinical study staff. The date, time, dosage, and location of each injection will be recorded by the clinical staff. Study staff will address non-adherence with the patient as needed.

Adherence to oral medication will be rated by a team of research assistants who will not inform the clinical team of their ratings or determinations. The oral antipsychotic medication adherence ratings will rely primarily on pill counts. Patients will be asked to bring their pill bottles to clinic appointments, for pills to be counted by a separate, nonclinical staff. Medication possession information will be captured through the pharmacy voucher billing and used as an additional source of information in the all sources consensus adherence ratings. Adherence ratings will be a consensus rating based on all sources of information (pill counts, plasma assays, patient self-report, clinician judgment based on the occurrence or change in side effects, family or caregiver collateral information, and pharmacy billing). Retroactive changes to the all sources consensus adherence ratings based on new information is allowed. No changes will be made to the quantitative pill counts based on changes in the patient or caregiver reports. Oral medication adherence will also be tracked in this way for any other oral antipsychotic medications if the initially assigned ARI-ORAL medication needs to be switched.

8.3. Study Drug Dose Adjustment and Stopping Rules

8.3.1. Aripiprazole Prospective Tolerability Screening

After Screening but before Randomization (Stabilization period), the patient's current and past medication history will be reviewed carefully. Patients with current or prior exposure to oral aripiprazole meeting criteria of a reliable history at least two weeks given at >10 mg day for a two-week period will be assessed for their efficacy and tolerability to aripiprazole.

Tolerability path will involve flexibly dosed aripiprazole prescribed ≥ 2 weeks. Patients will be eligible for Randomization upon completing this (and other) required screening procedures.

8.3.2. Cross-Over from Other Oral Antipsychotics

For patients on other [non-aripiprazole] oral antipsychotics, the clinician and patient can choose a cross-taper switch plan ranging from immediate discontinuation to a delayed cross-over during Stabilization period.

8.3.2.1. Other Concomitant Medications

Most adjunctive psychotropic medications can be continued during the cross-over and after the cross-over. Patients receiving anti-EPS or anti-akathisia medications will have these medications continued for at least 30 days and then will be evaluated for possible taper and discontinuation if the patient has been on ARI-ORAL for \geq 30 days without EPS or akathisia.

